Inappropriate Drug	Any medication discrepancies that do not fit into any of the previously mentioned categories, such as a medication that no longer needed but is reordered in new prescription; a different formulation of the same item is prescribed.	Example 1:  A patient had diarrhoea in the ward and was given oral Loperamide 2mg TDS or PRN. However, Loperamide 2mg TDS was written on the discharge prescription when the patient no longer had diarrhoea.  Example 2:  A patient has been discharged with Chloramphenicol ear drops. However, the patient has an eye infection and was treated with Chloramphenicol eye drops in the ward.

Table 2.2:Description And Example Of Each Type Of Medication DiscrepancyIdentified During Medication Reconciliation At The First Follow-Up At HealthClinics After Discharge From The Hospital

Type of Medication Discrepancy	Description	Example
Discrepant dose	A different dosage of a medication is prescribed in the new prescription compared to the discharge prescription.	A patient has been discharged with Losartan 100mg. However, the new prescription on the first visit to the health clinic is Losartan 50mg.
Discrepant frequency	A different frequency of medication prescribed in the new prescription compared to the discharge prescription.	Ü
Polypharmacy	Multiple agents from the same therapeutic class.	Mefenamic acid and Diclofenac are prescribed concurrently.
Drug Omission	Medication is not prescribed in the new prescription but is listed in the discharge prescription.	A patient was discharged with Metoprolol, Losartan, and Metformin. However, only Metoprolol and Metformin are prescribed in the new prescription on the first visit to the health clinic.

Table 2.2 continued

Drug	Medication is prescribed in the	On the first visit to the health clinic,
Addition	new prescription but not listed in	the patient is prescribed with
	the discharge prescription.	Metoprolol, Losartan and
		Metformin. However, only
		Metoprolol and Metformin are listed
		in the discharge medication list.
Inappropriate	Any medication discrepancies that	Example 1:

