### 2.5 Sample Size Calculation

This study aims to compare the prevalence of medication discrepancies in the first prescription upon transition of care from hospitals to primary health clinics between MedBook Portal and standard care. Hence, a two-tailed z-test of proportion between two groups with 80% power and a 5% of level significance will be used (10). The prevalence of medication discrepancies upon discharge reported in a previous study is 49% (8). We estimate the reduction of medication discrepancies via implementation of MedBook is 15%. Thus, a sample size of 322 subjects, 161 subjects in each group, is sufficient to detect a clinically importance difference of 15% between groups. However, with the estimation of a 20% loss to follow up, a total of 386 subjects will be recruited.

In addition, this study also aims to ascertain the prevalence of medication discrepancies and type of medication discrepancies in discharge prescription and in the first prescription upon transition of care from hospitals to primary health clinics. Sample size is calculated by using the following formula (11):

$$n = \frac{Z^2 P(1-P)}{d^2}$$

where n = sample size,

Z = Z statistic for a level of confidence,

P = expected prevalence or proportion

d = precision

By determining the Z = 1.96 for 95% CI and d = 0.05, the minimum sample size is 384. Based on the above sample size calculation, a total of 386 patients will be recruited. The sample size allocation for each hospital is determined on a pro-rata basis based on the total bed numbers in general medical wards and Bed Occupancy Rate (Table 2.4).

**Table 2.4:** Sample Size Allocation Of Each Hospitals

Public Major	Wards	Total	Bed	Sample
Hospitals		Bed	Occupancy	Size
		Numbers	Rate (%)	Allocation
Sarawak General	Male General Ward	48	114.4	144
Hospital	Female General Ward	48	102.0	
Sibu Hospital	Male General Ward 1	36	62.2	106
	Male General Ward 2	36	73.4	
	Female General Ward	32	83.5	
Miri Hospital	Male General Ward	29	114.1	72
	Female General Ward	30	62.8	
Sarikei Hospital	Male General Ward	35	82.4	64
	Female General Ward	35	50.2	
Total	-	329	-	386

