### 2.11 Intervention Group

MedBook Portal Notice will be attached in front of the patient's home-based medical card for the doctors and pharmacists at health clinics to identify the recruited patients. This appointment would be their first follow-up at health clinics after discharge from the hospital.

During the doctor's review of the patient in the intervention group, the doctor shall log in to the MedBook Portal to check on the discharge medication list and review the case based on the previous medical record in the home-based medical card and the discharge note if the patient hand over it to the doctors in their first review. Then, the doctor will conduct medication reconciliation by comparing the list of medications in the discharge prescription against the new prescription prepared.

Study pharmacists at the health clinics are required to screen patients' home-based medical cards presented to the pharmacy upon collecting medications. Once the pharmacists at health clinics identify the recruited patients via the MedBook Portal Notice, the pharmacist shall log in to the MedBook Portal to check the discharge medication list. The pharmacist shall conduct medication reconciliation by comparing the new prescription received against the discharge medication list in the portal. Intervention is to be carried out by the study pharmacists through confirmation with the doctor to determine the intentional or unintentional medication discrepancies.

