### 2.12 Control Group

Patients will receive the standard care in which doctors review patients based on the previous medical record in the home-based medical card and discharge note if the patient hands it to the doctors in their first review. Doctors cannot retrieve a patient's discharge medication list from MedBook Portal. No MedBook Portal Notice is attached to the patient's home-based medical card.

The principal investigator will provide a patient list in the control group to the study pharmacist at the health clinic. By knowing their appointment date, the study pharmacist shall search for the first prescription upon transitioning care from the hospital to the primary health clinic. Subsequently, the study pharmacist shall compare the discharge prescription in MedBook Portal with the first prescription to identify medication discrepancies. If any differences are detected, study pharmacists will confirm with the doctor to decide intentional or unintentional medication discrepancies. However, the study pharmacist might not be able to retrieve the first prescription immediately on the appointment date as there is no MedBook Portal Notice attached. As a result, the study pharmacist can only check with the prescriber on the discrepancy at a later time.

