### 2.14 Outcomes

The primary outcome of the study is the percentage of prescriptions with medication discrepancies in the first prescription during the first follow-up visit at the primary health clinic after hospital discharge. A comparison of the prevalence of prescriptions with medication discrepancies in the intervention group and the control group will be conducted.

The secondary outcome of the study is the percentage of prescriptions with medication discrepancies in the discharge prescription. This is measured before the intervention. In addition, the type of medication discrepancies and predictors associated with medication discrepancies in discharge prescriptions and the first prescriptions upon transitioning care from hospitals to primary health clinics will be collected. Predictors associated with medication discrepancies will be analysed using multiple logistic regression.

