# MedRecon Data collection Form (Health Clinic) \*Required 1. ID This ID is the ID assigned during the recruitment of the patient \*KK Sentosa KK Samarahan KK Samarahan KK Jalan Oya KK Samarahan KK Lanang KK Lanang KK Linang KK Sintangor KK Bintangor 3. Number of Medication \*

12. Type of Medication Discrepancies *	Mark only one oval.  Discrepant Dose  Discrepant Frequency  Dolypharmacy  Drug Omission  Drug Addition	13. Any other Medication Discrepancies? *  Mark only one oval.	14. Drug Name with Discrepancies *	15. Intentional or unintentional *  Mark only one oval.	Intentional  Unintentional
8. Type of Medication Discrepancies * Mark only one ovel	Mark only one oval.  Discrepant Dose  Polypharmacy  Drug Omission  Drug Addition  Inappropriate Drug	9. Any other Medication Discrepancies? *  Mark only one oval.  Yes  No	
 
Drug Name with Discrepancies *
 
	11. Intentional or unintentional *  Mark only one oval.	Unintentional

 
Type of Medication Discrepancies *
 
Mark only one oval.
 
	Discrepant Dose  Discrepant Frequency  Polypharmacy  Drug Omission  Inappropriate Drug	21. Any other Medication Discrepancies? *  Mark only one oval.  Yes  No	Drug #5  22. Drug Name with Discrepancies *	23. Intentional or unintentional *  Mark only one oval.  Intentional  Unintentional

 
Type of Medication Discrepancies *
 
Mark only one oval.
 
	Discrepant Dose  Discrepant Frequency  Polypharmacy  Drug Omission  Inappropriate Drug	17. Any other Medication Discrepancies? *  Mark only one oval.  Yes  No	Drug #4  18. Drug Name with Discrepancies *	19. Intentional or unintentional *  Mark only one oval.  Intentional  Unintentional

 
Type of Medication Discrepancies *
 
Mark only one oval.
 
	Discrepant Dose  Discrepant Frequency  Polypharmacy  Drug Omission  Drug Addition	29. Any other Medication Discrepancies? *  Mark only one oval.  Ves  No	Drug #7 30. Drug Name with Discrepancies *	31. Intentional or unintentional *  Mark only one oval.  Intentional  Unintentional

 
Type of Medication Discrepancies *
 
Mark only one oval.
 
	Discrepant Dose     Discrepant Frequency     Polypharmacy     Drug Omission     Drug Addition	25. Any other Medication Discrepancies? *  Mark only one oval.  \(\sum_{\text{Yes}}\)	Drug #6 26. Drug Name with Discrepancies *	27. Intentional or unintentional *  Mark only one oval.  Dintentional  Unintentional

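### The primary outcome counts prescriptions while patients are randomised, so a visit with no prescription at all has no scoring rule, capture differs by arm, and the expected 20% loss goes into an unexamined complete-case test

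*Combined protocol and SAP*

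**What the plan says.** Section 2.10 randomises patients 1:1. Section 2.14 defines the endpoint on another unit: "The primary outcome of the study is the percentage of prescriptions with medication discrepancies in the first prescription during the first follow-up visit". Table 2.2 in section 2.2.4 finds discrepancies by comparing the clinic prescription with the discharge prescription. Drug Omission, for example, is defined as: "Medication is not prescribed in the new prescription but is listed in the discharge prescription".

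The arms reach that comparison by different routes. In section 2.11 the clinic pharmacist recognises an intervention patient by the MedBook Portal Notice on "home-based medical cards presented to the pharmacy upon collecting medications". In section 2.12 the principal investigator supplies a list of control patients, and "the study pharmacist shall search for the first prescription upon transitioning care from the hospital to the primary health clinic".

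On losses, section 2.5 says "with the estimation of a 20% loss to follow up, a total of 386 subjects will be recruited". Section 2.4.3 withdraws patients readmitted before the visit and replaces nobody. Section 2.13 provides reminders. Section 2.15 names the chi-square test for categorical variables. It states no analysis set, no denominator, no rule for randomised patients without an outcome and no sensitivity analysis. The flow chart (Figure 2.5) is not reproduced in the available text, so any analysis box in it could not be checked.

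**The concern.** Three things follow from these passages.

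1. **Gap in the outcome rule.** A patient who loses one of three discharge drugs is an event. A patient who attends and leaves with no prescription at all has nothing to compare, and the plan does not say whether that patient is an event, a non-event or outside the denominator. Whether a prescription is written is decided after randomisation, at the visit where the intervention acts. Restricting the analysis to written prescriptions therefore conditions on something the intervention could change.

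2. **Unequal capture.** A patient who attends but does not collect medicines has a stated route to capture only in the control arm.

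3. **Unexamined loss.** The planned test uses whoever has a scored prescription. That is valid only if the discrepancy rate in each arm is the same among unscored as among scored patients, and the plan provides no way to examine this.

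At stake is whether the reported difference describes the randomised groups, and whether a reader could tell how far it depends on patients who were not seen.

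**Working it through.** **Size of the loss.** The plan's 386 is 322 × 1.2 = 386.4, so the allowance can be read in two ways:
- 20% of those recruited: 386 × 0.20 = 77.2, about 39 per arm, leaving 193 − 39 = 154 scored per arm.
- The excess over 322: 386 − 322 = 64, or 32 per arm, leaving 161 scored per arm.

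**Complete-case result at the plan's rates (49% v 34%, section 2.5).** 0.49 × 154 ≈ 75 and 0.34 × 154 ≈ 52. The test is the pooled two-proportion z-test, equivalent to the chi-square test without continuity correction. The difference is 75/154 − 52/154 = 14.9 points. The pooled proportion is 127/308 = 0.412, SE = √(0.412 × 0.588 × 2/154) = 5.6 points, z = 2.66, p = 0.008.

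**Adding the 39 unscored patients per arm.** With assumed rates r_C (control) and r_I (intervention) among the unscored, compare (75 + 39 r_C)/193 with (52 + 39 r_I)/193.

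| Unscored control | Unscored intervention | Difference (points) | p |
|---|---|---|---|
| 20% | 20% | 11.9 | 0.015 |
| 49% | 49% | 11.9 | 0.018 |
| 80% | 80% | 11.9 | 0.019 |
| 49% | 58% | 10.1 | 0.046 |
| 49% | 60% | 9.7 | 0.055 |
| 34% | 44% | 9.9 | 0.048 |
| 34% | 46% | 9.5 | 0.058 |

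Equal rates mean no benefit at all among the unscored, and the result still holds. In two-point steps it is lost at gaps of 60 − 49 = 11 and 46 − 34 = 12 points. In one-point steps p first passes 0.05 at 59% v 49% (0.0501) and 45% v 34% (0.053), a point lower in each case.

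**The smaller loss.** With 32 unscored per arm and 79/161 v 55/161 scored, significance is lost at about 65% v 49% (p = 0.053) or 50% v 34% (p = 0.051), gaps of about 16 points.

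These p-values treat filled-in outcomes as observed data. Allowing for that uncertainty would bring the tipping points somewhat lower.

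**Visits with no prescription at all.** The documents give no rate, so the shares u are assumptions. If such visits count as events, the rate in each arm is u + (1 − u) × observed rate, starting from 49% v 34% observed.

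| u control | u intervention | Rates | Difference (points) |
|---|---|---|---|
| 2% | 0% | 50.0% v 34.0% | 16.0 |
| 5% | 1% | 51.6% v 34.7% | 16.9 |
| 5% | 5% | 51.55% v 37.3% | 14.25 |

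These move the 15-point difference by roughly 1 to 2 points, against an SE of about 5.5. The most lopsided cases within 5% go a little further: 5% v 0% gives 51.55 − 34.0 = 17.55, and 0% v 5% gives 49.0 − 37.3 = 11.7.

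**Capture by arm.** If a prescription is written but not collected at the clinic pharmacy, the control search can find it, whereas section 2.11 has no step that would. If no prescription is written, the control search comes back empty for a known patient, so the gap is at least visible. In the intervention arm nothing prompts the pharmacist to look.

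**The case against.** A reader might infer that any visit at which no discharge drug is prescribed goes uncounted. The documents do not support that. If the clinic prescribes anything else, a new prescription exists and Table 2.2 scores each missing discharge drug as an omission. Only a visit with no prescription at all lacks a rule, and there the plan is silent; it does not exclude the visit. The clinic form in Appendix B is tied to the patient ("This ID is the ID assigned during the recruitment of the patient") and asks for a medication count, so a zero is not ruled out, though no instruction calls for one.

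A reader might also infer that intervention patients who collect nothing cannot be found. That is too strong. The coordinator's patient list carries group assignment and goes to the principal investigator for reminders (2.10), and clinic pharmacists can see both groups' discharge prescriptions in the portal (2.7.2). The means exist; section 2.11 does not tell anyone to use them.

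The strongest counter-argument concerns the loss. Death, non-attendance and going elsewhere come before the doctor opens the portal, reminders are not described as arm-specific, and nothing in the documents says why unscored intervention patients should do worse than unscored controls. The inference that the 20% loss will overturn a positive result is therefore unsupported: it takes a gap of about 11 to 12 points in the adverse direction, or about 16 on the smaller loss. The extreme bounds, (75 − 91)/193 = −8.3 to (114 − 52)/193 = +32.1 points, are what any trial with this much loss would show, and they carry little weight.

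What remains is the undefined visit, the arm-specific tracing and the absence of any stated analysis set or sensitivity analysis.

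**Conclusion.** The concern holds in limited form. As written, the denominator leaves a visit with no prescription at all unscored, the stated tracing can capture patients differently by arm, and the primary test is in effect a complete-case test with no check on the expected loss. This goes beyond missing detail, because following 2.11, 2.12 and 2.14 literally could bias the comparison.

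The likely size is modest. At the plan's own rates, a result of p = 0.008 stays at p = 0.015 to 0.019 for shared unscored rates from 20% to 80%. No-prescription visits shift the estimate by about 1 to 2 points in the main scenarios. These conclusions assume 49% v 34% among scored patients, equal loss in the two arms, and no-prescription shares of at most 5%. That last figure is an assumption the documents neither support nor contradict. A result closer to the significance boundary would be more fragile than this example.

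**What to change.** - **Section 2.14:** define the outcome as the percentage of randomised patients with a first clinic visit who have at least one discrepancy at that visit. Count an attended visit with no prescription at all as a Drug Omission for each discharge drug, with the usual intentional or unintentional tag.
- **Sections 2.11 and 2.12:** trace both arms from the same patient list and appointment dates, whether or not medicines are collected.
- **Appendix B:** add two answers, *attended, no prescription* and *no visit (reason)*.
- **Section 2.15:** state the analysis set. Report unscored patients by arm and reason (death, readmission, non-attendance, other facility). Beside the chi-square test, add a tipping-point table that varies the discrepancy rate among unscored living patients separately in each arm.

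Imputation from the pre-allocation Appendix A data is optional and may need software beyond the named jamovi version. It should not be applied to patients who died, for whom a clinic prescription does not exist and so is not a missing value.

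The cost is some wording, two form options, list tracing in the intervention arm and a short extra analysis, with no additional patients. The downside for the sponsor is that a positive result may be shown to depend on the patients who were not scored.

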### 1.5 Study Hypotheses

The study hypotheses are formulated based on the study specific objectives. For the first specific objective, the hypothesis is about the impact of MedBook Portal on the prevalence of medication discrepancies in the first prescription upon transition of care from hospitals to primary health clinics.

In terms of the second and third objectives, the hypotheses are based on the previous study conducted the hypotheses are based on the previous study conducted by Law and Chong (2017) in Malaysia. This study reported 49% of the discharge prescription were found to have a least one medication discrepancies (8).

For the fourth and fifth specific objectives, there are five variables are included as the secondary outcome of the study, namely age of patient, number of comorbidities, number of medications, type of medication (ATC categorization), and experience of prescriber (category of prescriber). All the five secondary outcomes are hypothesized to be the predictors of medication discrepancies. The hypotheses are tabulated in Table 1.1.

Table 1.1: Study Hypotheses

Specific objective 1: To assess the prevalence of medication discrepancies in the first prescription upon transition of care from hospitals to primary health clinics, comparing MedBook Portal to standard care.

H1a

There will be a significant difference of medication discrepancies rates between the intervention group and the control group after the intervention. The estimated difference of the medication discrepancies rates is 15%, with intervention group having lower medication discrepancies rates than control group.

Specific objective 2: To determine the prevalence of the type of medication discrepancies in the first prescription upon transition of care from hospitals to primary health clinics.

H2a

The prevalence of each type of medication discrepancy ranges from 5 - 60%, with Drug omission as the most common medication discrepancy in the first prescription upon transition of care from hospitals to primary health clinics.

Specific objective 3: To determine the prevalence of the type of medication discrepancies in discharge prescription.

Н3а

The prevalence of each type of medication discrepancy ranges from 5-60%, with Drug omission as the most common medication discrepancy in discharge prescription.

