# 2.4 Study Sample and Locations

This study will be conducted in four public tertiary hospitals and ten public primary health clinics. The four public hospitals that cater for the patients from southern, central, and northern zones in Sarawak are selected. Those are Sarawak General Hospital (southern zone), Sibu Hospital, Sarikei Hospital (middle zone) and Miri Hospital (northern zone).

During this study, ten public primary health clinics which are located nearby to the four selected hospitals are chosen to follow up the participants who will be discharged and referred to these clinics. The healthcare facilities involved in this study are presented in Table 2.3. All patients who fulfil the selection criteria mentioned later will be invited to participate in the study.

**Table 2.3:** Public Major Hospitals and Health Clinics Involved in this Study

Public Major Hospitals	Public Primary Health Clinics
Sarawak General Hospital	Batu Kawa HC, Kota Sentosa HC, Kota Samarahan HC
Sibu Hospital	Jalan Oya HC, Lanang HC, Sibu Jaya HC
Miri Hospital	Miri HC, Tudan HC
Sarikei Hospital	Sarikei HC, Bintangor HC

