# 2.15 Data Analysis

All data will be analysed using The jamovi project (2022) (Version 2.3). Descriptive statistics (frequency and percentage; mean and standard deviation) will be used to describe the socio-demographic characteristics of the participants.

Categorical variables, expressed as numbers and percentages, are compared by the Chi-square test. Continuous variables will be tested for normality using One-Sample Kolmogorov-Smirnov Test and compared using independent t-test for normally distributed data and the Mann-Whitney U test for non-normally distributed data. Data with normal distribution are reported as mean (standard deviation, SD), while non-normally distributed variables are reported as median (interquartile range, IQR).

The predictors associated with medication discrepancies will first be analysed using univariable logistic regression. The variables with p-value <0.1 by univariable analysis will be included in the multivariable logistic regression model. All statistical tests are two-tailed and p<0.05 is set to be statistically significant.

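### The predictor models for objectives iv and v pool four hospitals and ten clinics with no site term, so site differences can be read as effects of prescriber category or another predictor

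*Combined protocol and SAP*

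**What the plan says.** Section 2.4: "This study will be conducted in four public tertiary hospitals and ten public primary health clinics". Table 2.4 allocates the 386 patients to the hospitals as 144, 106, 72 and 64.

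Section 1.5, on objectives iv and v, says "there are five variables are included as the secondary outcome of the study": age, number of comorbidities, number of medications, ATC type of medication and prescriber category. H4a and H5a use the same five. Site is not among them.

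Section 2.14: "Predictors associated with medication discrepancies will be analysed using multiple logistic regression". Section 2.15 gives the steps: "The predictors associated with medication discrepancies will first be analysed using univariable logistic regression", then "The variables with p-value <0.1 by univariable analysis will be included in the multivariable logistic regression model". The threshold is general: "All statistical tests are two-tailed and p<0.05 is set to be statistically significant".

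No section names hospital or clinic as a covariate, stratum, random effect or cluster. The data collection forms (Appendices A and B) do carry a list of clinics.

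**The concern.** Objectives iv and v are observational. Patients are not randomised to a prescriber grade or to a length of medication list, so the 1:1 allocation does not protect these estimates.

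The documents give reasons why sites may differ:
- Bed occupancy by ward in Table 2.4 runs from 50.2% to 114.4%.
- Under section 2.13, the hospital sets the interval to the first clinic visit.
- Discrepancies are found by each site's own study pharmacist and settled with the prescriber, and section 2.10 says that neither is blinded. Site is therefore partly an assessor effect.

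If a site with a higher recorded rate also has more junior prescribers, the pooled model gives prescriber grade an odds ratio away from 1 even when grade has no effect within any site. This shifts the estimate itself, apart from any effect of clustering on its standard error. Because site is not a listed candidate, the p<0.1 screen as written does not bring it in.

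What is at stake is the use of the results. Section 1.8 wants professionals to prioritise patients for reconciliation. An odds ratio that points to a prescriber grade when the difference lies between hospitals or assessors would misdirect that effort.

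**Working it through.** **Inputs from the documents.** Hospital sizes are 144/106/72/64 (Table 2.4). They reproduce within 1 from beds × occupancy: occupied beds are 103.9, 75.5, 51.9 and 46.4 (total 277.7), so 386 × share = 144.4, 105.0, 72.2 and 64.5. The same figures give bed-weighted occupancy of 103.9/96 = 108% (Sarawak General), 75.5/104 = 73% (Sibu), 51.9/59 = 88% (Miri) and 46.4/70 = 66% (Sarikei).

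**Inputs assumed.** The documents give no discrepancy rates or prescriber mix by hospital. The values below are assumptions, chosen to show a range. Prescriber category is reduced to junior or senior, with no effect of grade within any hospital.

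**Formula.** For hospital h with size n, rate r and junior share s, pooled junior events are a = Σ n·s·r out of J = Σ n·s, and pooled senior events are b = Σ n·(1−s)·r out of S = Σ n·(1−s). The pooled OR is [a/(J−a)]/[b/(S−b)]. The standard error of log OR is √(1/a + 1/(J−a) + 1/b + 1/(S−b)). With λ = log OR/SE, the chance of p<0.05 is about Φ(λ−1.96) + Φ(−λ−1.96).

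**One case in full.** Rates 60/47/42/38%, junior shares 75/60/50/40%:
- J = 108 + 63.6 + 36 + 25.6 = 233.2; a = 64.8 + 29.9 + 15.1 + 9.7 = 119.5 (51.3%).
- S = 36 + 42.4 + 36 + 38.4 = 152.8; b = 21.6 + 19.9 + 15.1 + 14.6 = 71.2 (46.6%).
- OR = 1.20, log OR = 0.186, SE = 0.208, λ = 0.89, false positives 14.5%. Simulation gives 14–15%.

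**Range.** The last two columns are simulated false-positive rates without and with adjustment for hospital (indicators or stratification).

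| Rates by hospital (%) | Junior share (%) | Pooled OR | Formula | Simulated, no site | Simulated, with hospital |
|---|---|---|---|---|---|
| 60/50/40/35 | 60 at each | 1.00 | 5.0% | 4.8% | 5.0% |
| 55/50/45/40 | 70/60/55/50 | 1.07 | 6.2% | 5.7% | 4.8% |
| 60/47/42/38 | 50/60/40/75 | 0.94 | 6.2% | about 6% | not run |
| 60/35/50/40 | 60/50/80/40 | 1.12 | 8.6% | 9.0% | 5.4% |
| 60/47/42/38 | 75/60/50/40 | 1.20 | 14.5% | 14–15% | about 5% |
| 60/50/40/35 | 80/60/50/40 | 1.28 | 21.6% | 20.6% | 5.2% |
| 35/40/50/60 | 80/60/50/40 | 0.80 | 18.6% | 18.7% | 4.9% |

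Changing the last rate in the second row to 42% gives OR 1.06 and about 6%.

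**With the screen and two null predictors.** Prescriber category and list length were simulated together through the p<0.1 screen and the multivariable model. The nominal chance of at least one false predictor is 1 − 0.95² = 9.75%. Site standard deviations (outcome/predictor) are on the logit scale for the outcome and prescriber category, and in SD units for list length. Without and with site terms:
- Four hospitals: 10.1% and 10.1% (0.2/0.3); 12.6% and 9.3% (0.3/0.5); 18.7% and 9.6% (0.5/0.5).
- Ten clinics, 309 patients: 9.9% and 9.9%; 12.6% and 10.8%; 13.7% and 9.1%, for the same three settings.

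**Room for the term.** At the plan's rates there are about 386 × 0.49 = 189 discharge events. At the clinic there are about 309 × 0.415 = 128, taking 386 × 0.8 = 309 patients and (0.49 + 0.34)/2 = 0.415.

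**The case against.** Several points on the other side have force.

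- **Both conditions are assumed.** Distortion needs sites to differ in rate and in predictor mix. With the same mix everywhere there is none. Reordering the junior shares takes the 14–15% case down to about 6%. This stands, and it limits the claim to what can happen. A reader might infer that site differences will in fact be reported as prescriber effects; the documents hold no site-level figures that would show it.
- **The final model is multivariable.** Age, comorbidities and number of medications, if they pass the screen, may absorb some between-site case mix. This is fair. They would not absorb differences in detection between pharmacists.
- **The aim is associational.** A pooled association is a legitimate target for screening patients. This stands in part, but differential detection by site would still bias the pooled odds ratio as a description of true discrepancies.
- **Section 2.15 lists no variables.** It refers only to predictors and variables, and section 2.7.1 also collects gender. A reader might infer that the plan rules site out; it is only silent. Silence still leaves the choice to be made after the results are seen.
- **Hospital may not follow from clinic.** A reader might take Table 2.3 as mapping every patient to one hospital. It lists clinics beside hospitals, but nothing says that a hospital refers only within its row. This stands and changes the fix.

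A reader might also infer that the MedBook comparison is confounded by site. It is not in this sense, because allocation to the two groups is randomised.

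**Conclusion.** The concern holds as a possibility that the plan leaves open, not as a demonstrated bias. The omission is a fact of the text. Its effect on a null two-level prescriber variable, under assumed site differences at the Table 2.4 sizes, runs from none to roughly a three- to fourfold false-positive rate. The prescriber variable on the forms has more than two levels, and the single-predictor figures come from a model without the other candidates, so they show scale and are not forecasts.

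The point is worth acting on because nobody can know beforehand whether the sites differ. In the single-predictor simulations a hospital term held the error near 5% whether they did or not. It concerns secondary objectives iv and v only.

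**What to change.** In section 2.15:
- Force hospital (3 df) into the discharge-prescription model, whatever its p-value.
- Force hospital, or a clinic random intercept, into the first-prescription model in the same way.
- Keep these terms outside the p<0.1 screen and include them in the single-predictor models too.
- Report the predictor odds ratios as within-site associations, and name differences in detection between pharmacists as a limitation.

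Take the discharging hospital from enrolment or randomisation records, not from Table 2.3. The clinic is already on both forms.

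The cost is a change of wording, a few parameters and a small loss of precision. Three parameters are modest against about 189 and 128 events, but the multi-level ATC and prescriber factors draw on the same events, so the total number of parameters should be counted when the models are specified.
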